20.0 ALLOCATION

Identification and allocation of patients

A patient identification number will be assigned after consent has been signed.

Patients will be allocated to placebo or yFFP (ratio 1:1) by Trial Manager.

21.0 BLINDING

In the event of an urgent need to unblind treatment, call the Trial Manager.

If unblinding occurs, details including patient study number, the date performed, people involved, and the reason for the unblinding, shall be recorded by the administering nurse and retained.

If clinically indicated, the participant will be withdrawn from the medication.

Accidental unblinding's will be dealt with on a case by case basis if and when they arise. The patient's data should continue to be collected according to the visit schedule, even in the event of unblinding or withdrawal from study medication, unless the patient refuses.

22.0 STUDY DATA

Database

**INTRAVENOUS young FRESH FROZEN PLASMA (yFFP®) INVESTIGATIONAL TREATMENT FOR
PARKINSON'S DISEASE
PROTOCOL FOR CONTROLLED STUDY**

Source data will be entered by authorized staff onto a password protected Excel spreadsheet. All data entered will be QA-verified against the source documents.

Database passwords, data handling and confidentiality/format of records

Database access will be strictly restricted through passwords to the authorized research team.

All participant contact/screening and recruitment data will be stored on spreadsheets on DropBox, which will have restricted access from password protected computers. Accrual data will be anonymized and collated by the Trial Manager. No identifiable data will be transferred.

At the end of the study, essential documentation will be archived in accordance with sponsor and local requirements. The retention of study data will be the responsibility of the Principal Investigator.

23.0 ON-SITE/CENTRAL MONITORING

The Trial Manager will conduct on-site/central monitoring.

The Statistician may identify data fields that should be checked against the source data during site monitoring visits, where there are data queries, the research nurses will be responsible for resolving the queries.

The QA will review responses before closing the query.

24.0 STATISTICAL CONSIDERATIONS

Data analysis will be performed using a password-protected computer independent of study sponsor or clinical sites.

25.0 STATISTICAL ANALYSIS

A comprehensive statistical analysis plan will be developed and agreed upon with the trial's oversight committees. Section 26 contains a tentative outline for the statistical analysis of the UPDRS scores.

26.0 EFFICACY

Primary analysis

The sum of UPDRS subscales 1-3 will be considered as a summary of disease severity. For the various patients, differences between the baseline sums and sums at 24 weeks give summaries of disease severity change over the course of the study. The population of yFFP differences will be compared with the population of differences for the placebo patients. Past studies have found that sums of

**INTRAVENOUS young FRESH FROZEN PLASMA (yFFP®) INVESTIGATIONAL TREATMENT FOR
PARKINSON'S DISEASE
PROTOCOL FOR CONTROLLED STUDY**

UPDRS scores are normally distributed. An initial comparison between yFFP and placebo will then be afforded by a simple t-test. In view of the small sample size and the categorical nature of the data, other analyses will be explored. Those additional analyses may include a permutation test or other bootstrap methodology.

Secondary analysis

Changes in the three UPDRS subscales 1-3 will also be analyzed separately. Additional analysis will be performed as dictated by data exploration. End scores may be modeled as a function of initial scores and lab tests. The possibility of using the 12-week scores in a longitudinal model will be considered.

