2.0 SCOPE

Sample Size: 20 patients

10 patients will be designated to receive yFFP

10 patients will be designate to receive the placebo - .9% Saline with Riboflavin (Vitamin B2) additive

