7.0 STUDY DESIGN & METHOD

The study is a prospective double-blind placebo-controlled trial, designed to evaluate the safety and efficacy of intravenous young Fresh Frozen Plasma at 12.5 ml/kg in each of two doses, two days apart (25 ml/kg total).

Patients in the Placebo group will receive infusions of 0.9% Sodium Chloride with Vitamin B2 at a volume rate equal to that of yFFP 12.5 ml/kg in each of two doses, also two days apart.

Consecutive patients are alternately assigned to one of the two treatment study groups, labeled 'yFFP' or 'Saline' group. Because yFFP is in short supply,

**INTRAVENOUS young FRESH FROZEN PLASMA (yFFP®) INVESTIGATIONAL TREATMENT FOR
PARKINSON'S DISEASE
PROTOCOL FOR CONTROLLED STUDY**

the trial manager is free to change the strict alternate allocation sequence, according to the blood types of yFFP available.

Each participant's condition will be classified as mild to moderate. Patients above 2.5 on the Hoehn and Yahr scale will not be eligible for the trial.

The primary outcome is the change in sum of the UPDRS scales 1-3 in the yFFP group compared with the placebo group.

There will be one study site, a secondary care clinic specializing in neurology and infusions (Houston, Texas).

Study will include 20 patients with Parkinson's disease.

Blinding will be achieved by preparing both yFFP and placebo (0.1% Riboflavin in normal saline) solution into identical bags. The Riboflavin is added to achieve indistinguishable color when compared to the yFFP. Labels, barcoded numbers and expiration dates for both the active and saline placebo will be indistinguishable. All infusion bags will be masked.

For the time frame, study day 0 is defined as the day of treatment allocation. Baseline evaluation and laboratory testing will be done then. The first infusion will be scheduled at most two weeks later, and the second infusion will occur two days after the first.

Physician assessments, caregiver surveys and blood tests will be completed at 4-weeks, 12-weeks and 24 weeks, to explore the duration of yFFP - and unspecific treatment effects.

Definition of end of study

The end of the study will be the last participant's final contact at 24 weeks.

The study duration will be eight months from study set-up to analysis and closure. An interim report will be produced at the 12-week point.

Serious Adverse Events (SAE) will be monitored for 14-days after final dose of yFFP or until resolution.

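### The only firm primary test is an unadjusted change-score t-test; adjusting for the baseline UPDRS sum, often but not always more precise, is left optional and secondary

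*Combined protocol and SAP*

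**What the plan says.** The primary outcome is set in Section 7.0: "The primary outcome is the change in sum of the UPDRS scales 1-3 in the yFFP group compared with the placebo group". Section 26.0, under its primary-analysis heading, takes each patient's difference between the baseline and 24-week sums and states: "An initial comparison between yFFP and placebo will then be afforded by a simple t-test". Other methods, such as a permutation test or bootstrap, are mentioned only as possibilities, and none is said to adjust for baseline.

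Baseline enters as a predictor only under the secondary-analysis heading: "End scores may be modeled as a function of initial scores and lab tests". That sentence names no treatment term, so it may describe a prognostic model and not a treatment comparison.

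The outline is not final. Section 25.0 says "A comprehensive statistical analysis plan will be developed and agreed upon" and adds "Section 26 contains a tentative outline for the statistical analysis of the UPDRS scores".

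The baseline needed for adjustment is taken on day 0, the day of allocation (Section 7.0): "Baseline evaluation and laboratory testing will be done then". It is already required to compute the change score.

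**The concern.** A change score subtracts the whole baseline value, which amounts to fixing the slope of follow-up on baseline at 1. If the true slope is below 1, the subtraction overcorrects. The estimate then carries part of any baseline difference between the arms, with extra variance. Regression on baseline estimates the slope, at the cost of one degree of freedom.

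This matters because the trial is small. Section 2.0 gives "Sample Size: 20 patients", 10 per arm, and Section 27.0 bases that number on who was available, with no power target. Fewer may be analysed, because Section 11.0 withdraws patients whose infusion has not been given by day 5.

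Allocation adds a second reason to look at baseline. Section 7.0 describes alternation and then says "the trial manager is free to change the strict alternate allocation sequence, according to the blood types of yFFP available". A baseline gap may therefore not be due to chance.

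**Working it through.** **Inputs from the documents:** 20 patients, 10 per arm (Section 2.0); outcome and test as described in Sections 7.0 and 26.0. The plan gives no power or precision figure to reproduce.

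**Assumptions, because the documents are silent:** two-sided 5%; bivariate normal scores; equal arms; correlation rho between the baseline and 24-week sums from 0.5 to 0.95; SD ratio k = SD24/SD0 from 0.9 to 1.2. Steps 1 to 4 assume random allocation; step 5 drops that. N is the total analysed and n the number per arm.

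**1. Power of the planned t-test.** For an effect of 1 SD of change, the noncentral t with N - 2 df and noncentrality sqrt(N/4) gives 56% with N = 20, 51% with 18 and 46% with 16.

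**2. Average variance ratio, adjusted over change score.**

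Ratio = k²(1 - rho²) / (k² + 1 - 2 rho k) × (1 + 1/(N - 4))

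The last factor is the price of estimating the slope. With k = 1 and N = 20 this becomes (1 + rho)/2 × 17/16; for example, rho 0.7 gives 0.85 × 1.0625 = 0.90.

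| k | rho 0.5 | 0.7 | 0.8 | 0.9 | 0.95 |
|---|---|---|---|---|---|
| 0.9 | 0.71 | 0.80 | 0.84 | 0.86 | 0.84 |
| 1.0 | 0.80 | 0.90 | 0.96 | 1.01 | 1.04 |
| 1.1 | 0.87 | 0.98 | 1.03 | 1.06 | 1.04 |
| 1.2 | 0.93 | 1.03 | 1.06 | 1.04 | 0.93 |

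Adjustment loses on average when rho is above 0.88 (k = 1), between 0.74 and 0.97 (k = 1.1) or between 0.64 and 0.93 (k = 1.2), and never at k = 0.9. The average loss cannot exceed 1/(N - 4): 6.3% with N = 20, 7.1% with 18 and 8.3% with 16. The k = 1 break-even, 2/(1 + 1/(N - 4)) - 1, is 0.88, 0.87 and 0.85. Simulation agrees with the k = 1 row (0.795, 0.893, 0.959, 1.011, 1.033).

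**3. Power with adjustment, same effect, N = 20** (noncentral t with 17 df, averaged over baseline draws), against 56% for the t-test:

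| k | rho 0.5 | 0.7 | 0.8 | 0.9 | 0.95 |
|---|---|---|---|---|---|
| 1.0 | 66% | 60% | 58% | 56% | 55% |
| 1.1 | 62% | 57% | 55% | 54% | 54% |
| 1.2 | 59% | 55% | 54% | 55% | 59% |

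**4. A single trial with a chance baseline gap d (in baseline SDs).** The standard error of d is sqrt(2/10) = 0.447, so |d| exceeds 0.5 with probability 26% and 1 with probability 2.5%. The change score carries the fraction 1 - rho k of the gap. With k = 1 and rho 0.7 that is 0.3 × d, or 0.15 and 0.30 SD for gaps of 0.5 and 1 SD.

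- The variance of the adjusted estimate rises by the factor 1 + (n/2)d²/(N - 4): 1.08 and 1.31 for the two gaps. One trial can therefore lose more than the average cap.
- The change-score mean squared error is (1 - rho²)(2/n) + (1 - rho)²d². At rho 0.7 and d = 0.5 this is 0.102 + 0.0225 = 0.1245; the adjusted value is 0.102 × 1.078 = 0.110, a ratio of 0.88. At d = 1 the ratio is 0.134/0.192 = 0.70. At rho 0.9 the ratios are 1.01 and 1.04; at rho 0.95 they are 1.04 and 1.16.
- At rho 0.7, the mean 95% CI width moves from 1.44 (change score) to 1.38 (adjusted) baseline SDs with a 0.5 SD gap, but from 1.44 to 1.52 with a 1 SD gap.
- The t-test's type I error given the gap, at rho 0.7, is 5.3% or 11.2%. Over all randomisations it is 5%.

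**5. A systematic gap of 0.5 or 1 SD, rho 0.7, k = 1.** If the arms regress to a common mean, the change-score type I error is 7.0% or 13.0%, and the adjusted analysis holds 5%. If the arms differ stably, the adjusted analysis has 7.0% or 12.1%, and the change score holds 5%. Bias does not favour either method.

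**The case against.** The strongest reply is that a valid test matching the stated outcome is a defensible choice, and that the gain cannot be predicted. Adjustment loses in 8 of the 20 cells in the step 2 table, and in 6 of the 10 with k above 1. Entry is capped on Hoehn and Yahr stage and on disease duration (Section 9.0), while nothing caps the 24-week score, so k above 1 is plausible. This is suggestive only: neither cap is on UPDRS, and restricted entry may also lower rho. The low power comes mainly from having 20 patients; at k = 1 and rho 0.7, adjustment lifts it only from 56% to 60%. The precision figures assume random allocation, which Section 7.0 does not provide. The outline is tentative and calls the t-test initial, and Section 5.0 lists the trial as closed in January 2019.

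All of this stands as a limit on the size of the point. It does not overturn it. Over the range shown, the average variance gain reaches 29% and the average loss cannot exceed 6.3% with 20 analysed. The promised SAP is the natural place to settle the matter. If adjustment stays optional, the choice between two estimates could follow the results. Since allocation leaves the direction of bias open, both estimates should be shown.

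**Conclusion.** The concern holds. The one test the outline commits to leaves baseline unadjusted, and a baseline-adjusted treatment estimate is not firmly specified anywhere. This is a less efficient choice, not an error, and its weight is modest. With equal SDs and 20 analysed, adjustment saves 20% of the average variance at rho 0.5 and 10% at rho 0.7, and costs 1% to 4% at rho 0.9 to 0.95. With a larger SD at 24 weeks, the range of small losses widens. These results rest on assumed correlations and SD ratios, approximate normality and random allocation. The allocation rule does not favour either method on bias; it is a reason to report both.

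**What to change.** In the SAP promised in Section 25.0:

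- Make the primary analysis a linear regression of the 24-week UPDRS 1-3 sum on arm and baseline sum, two-sided 5%, reporting the adjusted difference with its 95% CI. Regressing the change on the same terms gives the identical arm estimate, so the outcome in Section 7.0 is kept.
- Name the change-score t-test and the permutation test as sensitivity analyses.
- Report the adjusted and change-score estimates side by side with the baseline difference. State that neither is protected against systematic imbalance, and treat any gap between them as a limit on the conclusion.
- If data are already unblinded, add the adjusted analysis labelled as not pre-specified.

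The cost is SAP wording; no new data are needed. The downsides are one degree of freedom, an average variance cost of up to 6% with 20 analysed (7% with 18, 8% with 16), a larger cost in a trial with a large imbalance, and bias of its own if the arms differ stably.

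### The primary t-test uses only baseline-to-week-24 differences, and no analysis is committed for the earlier visits: no planned contrast addresses duration, and outcome-related loss that differs between arms would bias the result

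*Combined protocol and SAP*

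**What the plan says.** Section 7.0 defines the endpoint without naming a visit: "The primary outcome is the change in sum of the UPDRS scales 1-3 in the yFFP group compared with the placebo group". It schedules three follow-up visits ("Physician assessments, caregiver surveys and blood tests will be completed at 4-weeks, 12-weeks and 24 weeks") and gives their purpose: "to explore the duration of yFFP - and unspecific treatment effects". It also promises a report partway through: "An interim report will be produced at the 12-week point". Section 30.0 adds an investigators' meeting at 12 weeks to look at results. Neither place names an endpoint, contrast or method.

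Section 26.0 fixes the visit for the primary analysis: "differences between the baseline sums and sums at 24 weeks give summaries of disease severity change over the course of the study". The test follows: "An initial comparison between yFFP and placebo will then be afforded by a simple t-test". A permutation or bootstrap analysis may be added. On the intermediate visits the section has one sentence, under secondary analysis: "The possibility of using the 12-week scores in a longitudinal model will be considered". Week 4 does not appear in Section 26.0.

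The documents contain no rule for a missing 24-week score. The only analysis set named is the per-protocol set in Section 11.0. Section 25.0 describes Section 26.0 as provisional, with a full SAP to follow.

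**The concern.** Two gaps come from the same choice of using only the first and last scores.

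- **Duration.** Treatment is two infusions two days apart. A contrast at week 24 alone cannot separate no effect from an effect that appeared early and faded. The earlier visits were scheduled to explore this, but no planned comparison uses them.
- **Missing scores.** A t-test on baseline-to-week-24 differences needs both scores. A patient seen at week 12 and then lost contributes nothing to it, although the week-12 score says something about where that patient was heading. If patients doing badly are lost more often in one arm, the remaining patients make that arm look better than it is. With 10 patients per arm, one or two such losses are enough to move the estimate.

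**Working it through.** The documents state no dropout rate, SD, power or significance level, so there is no plan figure to reproduce. The size of the problem has to be shown over assumed settings.

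**Inputs from the documents.** 20 patients, 10 per arm (Section 2.0); 1:1 allocation (Section 20.0); t-test on baseline-to-week-24 differences (Section 26.0).

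**Assumptions.** No true effect. Changes from baseline are normal with SD 1, and a higher value means worse. The correlation ρ between week-12 and week-24 change is 0.5, 0.7 or 0.85. The test is two-sided at 5%.

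**Estimators.** With Y12 and Y24 the changes at weeks 12 and 24:

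- Completers' t-test: mean of observed Y24 on yFFP minus mean of observed Y24 on placebo.
- Using week 12: in each arm, mean observed Y24 + b × (mean Y12 of all patients − mean Y12 of those seen at week 24), with b the pooled within-arm slope. This stands in for a likelihood-based longitudinal model.

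**Step 1: a case that can be checked by hand.** Suppose the two yFFP patients with the worst week-12 change are lost and nobody is lost on placebo. The two largest of ten standard normal values average 1.539 and 1.001, so the other eight average −(1.539 + 1.001)/8 = −0.3175. Multiplying by ρ gives the expected bias at week 24:

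- ρ = 0.5: −0.16
- ρ = 0.7: −0.22
- ρ = 0.85: −0.27

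Simulation of 40,000 trials gives −0.158, −0.221 and −0.271, with type I error of 6.4-9.5%. Using the week-12 scores leaves a bias of at most 0.001 SD here, at almost the same standard error (0.467 against 0.466 at ρ = 0.7).

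**Step 2: a less extreme mechanism.** The chance of loss on yFFP rises with the week-12 change (logistic, slope 1.5 per SD, assumed). Placebo loses 5% at random.

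| Loss on yFFP | Bias of t-test towards yFFP (ρ 0.5 to 0.85) | Bias using week 12 |
|---|---|---|
| 10% | 0.06-0.10 SD | about 0 |
| 25% | 0.14-0.24 SD | about 0 |

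Type I error is 5-7%. The standard error follows from the expected numbers of completers:

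- 10% loss: √(1/9 + 1/9.5) = 0.465 SD
- 25% loss: √(1/7.5 + 1/9.5) = 0.488 SD

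Across simulations it is about 0.46-0.49 SD. The bias is therefore at most about half a standard error.

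**Step 3: where the result changes.**

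- Equal outcome-driven loss in both arms (15% or 25%): bias of the t-test about 0.
- 25% loss on yFFP that depends on the week-24 score itself: bias of the t-test about 0.28 SD, and 0.08-0.21 SD remains after using the earlier score.
- Loss unrelated to scores: no bias, and a precision gain from the earlier visits of under 1%.

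The near-zero bias in Steps 1 and 2 is a consequence of the mechanism: loss was made to depend only on a score that was observed.

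**The case against.** The strongest reply is that no harm has been shown. The documents report no dropout and no imbalance in it. The infusions are over within days, so little treatment is left to abandon. Sections 16.0, 21.0 and 29.0 keep collecting data after infusions stop, after unblinding and after withdrawal from study drug. Section 26.0 is provisional and does not prescribe how missing 24-week scores are handled. The 12-week report and meeting, and the further exploratory analyses that Section 26.0 allows, may touch on duration. Duration is only something to explore, and Section 8.0 does not list it among the secondary outcomes. At n = 20, preferring a repeated-measures model to a t-test plus sensitivity analysis is partly a matter of taste.

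Much of this stands, and it rules out three stronger readings that a reader might infer:

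- **That dropout does bias the result.** The documents do not support this. The bias is conditional on loss that is related to outcome and differs between arms.
- **That the duration question will go unanswered.** The supportable statement is that no prespecified analysis addresses it.
- **That week-4 UPDRS scores will be in hand.** Section 7.0 speaks of physician assessments and does not say that UPDRS is scored at week 4. Only 12-week scores are implied, by Section 26.0.

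The reply does not remove the point. Continued follow-up reduces missing scores but does not say how to analyse those that remain, and Section 29.0 lets participants leave the study at any time. The 12-week report and meeting specify no analysis. An analysis chosen after looking at the data is not a planned one. The SAP still to be written is where the correction belongs.

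**Conclusion.** The point holds in conditional form. As outlined, the primary comparison rests on patients with a 24-week sum, week 12 is optional, week 4 is absent, and the purpose given for the intermediate visits has no planned analysis. These are facts of the text.

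The bias is a risk of modest size. Under the stated assumptions it is 0.06-0.10 SD at 10% and 0.14-0.24 SD at 25% outcome-driven loss on yFFP, with little inflation of type I error. Balanced loss, or loss unrelated to scores, gives essentially none. Using the earlier scores removes the bias at almost no cost in precision if data are missing at random. It removes only part if loss depends on the unseen week-24 score. It cannot help patients with no post-baseline score, such as those withdrawn before any infusion under Section 11.0. The plan should be changed on this point, but it does not by itself invalidate the trial.

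**What to change.** In the SAP:

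1. Confirm whether UPDRS is scored at week 4.
2. Commit to one baseline-adjusted repeated-measures model of the UPDRS 1-3 sum at weeks 12 and 24, and at week 4 if scored, with arm, visit and arm-by-visit terms. Name small-sample degrees of freedom and a simpler covariance structure as fallback.
3. Keep week 24 as the primary contrast. Report the earlier contrasts with confidence intervals as the exploratory duration analysis. Keep the t-test as a check.
4. State the missing-at-random condition and the model's limits: part of the bias remains if loss depends on the week-24 score, and patients with no post-baseline score are not helped.
5. Section 5.0 lists the trial as closed. If outcomes have already been seen, label the model post hoc.

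The cost is SAP wording and a little analysis time, using visits already scheduled. If UPDRS is not scored at week 4, the model runs on weeks 12 and 24; adding a week-4 score would change data collection. The downside is a somewhat more complex model at n = 20, with negligible gain in precision if dropout is unrelated to scores.
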